15.4 Study Monitoring

The Investigator will allow trial-related monitoring audits, ethics committee review, and regulatory inspection allowing direct access to the source data/documents.

15.5 Study Closure

Premature termination of the study by either Principal Investigator or Sponsor will be governed under the terms of the contract between both parties.

15.6 Study Record Retention

In accordance with SI 1928, the Sponsor and the Principal Investigator shall ensure that the documents contained, or which have been contained, in the trial master file are retained for at least 5 years after the conclusion of the trial and that during that period are:

- Readily available to the licensing authority on request; and
- Complete and legible.

All data derived from the study will remain the property of the Sponsor, Global Blood Therapeutics. The study will be the subject of a final clinical study report compiled by, or by order of the Sponsor.

All correspondence (e.g. with the Sponsor, ethics committee) relating to this study should be kept in the appropriate file folders.

Records of subjects source documents, CRF's, IMP inventory, pertaining to the study must be kept on file. Records must be retained according to the current ICH Guidelines on GCP.

The Sponsor and Principal Investigator shall ensure that the medical files of trial subjects are retained for at least 5 years after the conclusion of the trial. The Sponsor shall appoint named individuals within his organization to be responsible for archiving the documents which are, or have been, contained in the trial master file. Access to those documents shall be restricted to those appointed individuals. If there is transfer of ownership of data or documents connected with the clinical trial:

- The Sponsor shall record the transfer; and
- The new owner shall be responsible for data retention and archiving in accordance Statutory Instrument 1031 and amendments.

If the Principal Investigator moves, withdraws from an investigation or retires, the responsibility for maintaining the records may be transferred to another person who will accept responsibility. Notice of transfer must be made to and agreed by the Sponsor.

15.7 Publication Policy

After completion of the study, the Sponsor may prepare a joint publication with the Principal Investigator. The Investigator must undertake not to submit any part of the individual data from this protocol for publication without prior consent of the Sponsor at a mutually agreed time.

17.0 STUDY SCHEDULE

Table 4 Schedule of Assessments Group 1

Group 1: Subjects from Cohort 17 in the GBT440-001 study who have received GBT440 900mg per day for 4 months will continue receiving GBT440 900 mg per day for a further 2 months.

Assessments	Enrolment	Outpatient Treatment Period							
		1 a	15 +/-3 days g	30 +/-3 days	45 +/-3 days g	60 +/-3 days	67 +/-3 days	74 +/-5 days	88 end
Visit number	0	1		2		3	4	5	6
Informed consent	X	X							
Eligibility assessment	X	X							
Medical History	X								
Physical examination b	X		X	X	X				X
Weight	X		X	X	X	X			X
Vital signs	X	X	X	X	X	X			X
12 Lead ECG (single) c				X		X			X
Drug administration d		X				X			
Adverse events		X-----							-X
Urinalysis e	X		X		X				X
Urine microalbumin/creatinine	X								X
Haematology e	X		X	X	X				X
Serum biochemistry e	X		X	X	X				X
Coagulation e	X		X		X				X
Pregnancy test (females only)	X			X		X			X
Haemoglobin electrophoresis									X
PK samples (plasma and whole blood) f	X			X		X	X	X	X
Serum erythropoietin	X ^h			X		X			X
Exploratory plasma biomarkers	X ^h			X		X			X
Dense cells	X ^h			X		X			X
Carboxyhaemoglobin	X ^h								X
HbA1c	X ^h								X
NT-proBNP	X ^h								X
Concomitant medication diary	X-----								-X

Key

- a: Enrolment and visit 1 may be combined. On admission to the clinic the subjects will be asked whether they want to be considered for study GBT440-024. If the subject is interested in being enrolled on study GBT440-024 all consent activities will be completed before the samples/procedures for GBT440-001 or GBT440-024 are collected/Performed. Visit 0 (enrolment visit) is the last day of treatment in GBT440-001, which can be 6 days before Visit 1. If the last day of treatment in GBT440-001 (Day 118 or Day 60 for Cohort 17 and Cohort 15) – the enrolment visit is not being repeated as standalone visit.
- b: Complete physical examination on enrolment, a limited physical examination on all other days. Directed physical examinations will be performed as required.
- c: 12 lead ECG (single) will be performed within 30 minutes prior to dose
- d: GBT440 900 mg(three capsules) will be administered daily in the morning. On days when PK samples are drawn GBT 440 should be administered after an overnight fast.

During the dosing period subjects will be contacted every week in between out-patient visits to confirm GBT440 administration and subject well -being.

- e: Additional samples will be collected if clinically indicated
- f: PK samples will be drawn pre dose. If the dose is increased to 1500 mg, please collect the following timepoints: pre dose, then 1-4 hours, 6-8 hours and 24 hours post dose on study visit days of Day 15 (± 3 days), Day 60 (± 3 days) and Days 90 (± 3 days) of receiving 1500 mg.g: Days 15 and 45 are only to be conducted if the dose is increased to 1500 mg.
- h: Can be omitted if measurements were collected in the past 7 days as part of the GBT440-001 study.

Table 5 Schedule of Assessments for Groups 2, 4 and 5

Groups 2: Subjects from Cohort 17 in the GBT440-001 study who have received placebo for 4 months will receive GBT440 900mg per day for 6 months

Group 4: Subjects from Cohort 15 in the GBT440-001 study who have received placebo for 2 months will receive GBT440 900 mg per day for 6 months

Group 5: Subjects with SCD from Cohorts 7, 11, 12, 14, 16 or 17 in the GBT440-001 study will receive GBT440 900 mg per day for 6 months

Assessments	Enrolment a	Baseline for Cohort 7,11,12,14, 16 or 17 (within 7 days of Day 1)	Outpatient Treatment Period											
			1 +/-3 days a	15 +/-3 days	30 +/-3 days	45 +/-3 days	60 +/-3 days	90 +/-3 days	120+/-3 days	150+/-3 days	180 +/-3 days	187+/-3 days	194 +/-5 days	208 End
Day number	Last treatment day GBT440-001 (+6 days) Cohorts 15 and 17													
Visit number	0		1	2	3	4	5	6	7	8	9	10	11	12
Informed consent	X	X												
Eligibility assessment	X	X												
Medical History	X	X												
Physical examination b	X	X		X	X		X	X	X	X	X			X
Weight	X	X		X	X	X	X	X	X	X	X			X
Vital signs	X	X	X	X	X	X	X	X	X	X	X			X
12 Lead ECG (single) c	X	X			X		X	X	X	X	X			
Drug administration d				X-----							X			
Adverse events				X-----										X
Urinalysis e	X	X						X	X	X	X			X
Urine microalbumin/creatinine	X	X						X			X			
Haematology e	X	X		X	X	X	-	X	X	X	X			X
Serum biochemistry e	X	X		X	X	X	X	X	X	X	X			X
Coagulation e	X	X		X		X		X	X	X	X			X
Pregnancy test (females only)	X	X			X		X	X	X	X	X			X
Haemoglobin electrophoresis		X						X			X			X
PK samples (plasma and whole blood) f	X			X	X		X	X	X	X	X	X	X	X
Serum erythropoietin	X ^h	X			X		X	X	X	X	X			X
Exploratory plasma biomarkers	X ^h	X			X		X	X	X	X	X			X

Assessments	Enrolment a		Outpatient Treatment Period											
			1 +/-3 days	15 +/-3 days	30 +/-3 days	45 +/-3 days	60 +/-3 days	90 +/-3 days	120+/-3 days	150+/-3 days	180 +/-3 days	187+/-3 days	194 +/-5 days	208 End
Day number	Last treatment day GBT440-001 (+6 days) Cohorts 15 and 17	Baseline for Cohort 7,11,12,14, 16 or 17 (within 7 days of Day 1)	a											
Dense cells	X ^h	X			X		X	X	X	X	X			X
Carboxyhaemoglobin	X ^h	X						X			X			X
HbA1c	X	X						X			X			X
NT-proBNP	X ^h	X						X			X			X
Concomitant medication diary		X	X-----											X

Key

Note: Visit 0 is the last treatment day for subjects in GBT-440-001 (Day 118 for Cohort 17 and Day 60 for Cohort 15)

- a: Enrolment and visit 1 may be combined. On admission to the clinic the subjects will be asked whether they want to be considered for study GBT440-024. If the subject is interested in being enrolled on study GBT440-024 all consent activities will be completed before the samples/procedures for GBT440-001 or GBT440-024 are collected/Performed. Visit 0 (enrolment visit) is the last day of treatment in GBT440-001, which can be 6 days before Visit 1. If the last day of treatment in GBT440-001 (Day 118 or Day 60 for Cohort 17 and Cohort 15) – the enrolment visit is not being repeated as standalone visit.
- b: Complete physical examination on enrolment, a limited physical examination on all other days. Directed physical examinations will be performed as required.
- c: 12 lead ECG (single) will be performed within 30 minutes prior to dose
- d: GBT440 900mg(three capsules) for Group 2 and GBT 440 600mg (2 capsules) for Group 4 and GBT440 900 mg (3 capsules) for Group 5 will be administered daily in the morning. On days when PK samples are drawn GBT 440 should be administered after an overnight fast.
- During the dosing period, subjects will be contacted every week in between outpatient visits to confirm GBT440 administration and subject well being.
- e: Additional samples will be collected if clinically indicated
- f: PK samples will be drawn pre dose. If the dose is increased to 1500 mg, please collect the following timepoints: pre dose, then 1-4 hours, 6-8 hours and 24 hours post dose on study visit days of Day 15 (±3 days), Day 60 (±3 days) and Days 90 (±3 days) of receiving 1500 mg.
- h: Can be omitted if measurements were collected in the past 7 days as part of the GBT440-001 study.

Table 6 Schedule of Assessments Group 3

Group 3: Subjects from Cohort 15 in the GBT440-001 study who have received GBT440 600 mg per day for 2 months will continue receiving GBT440 600 mg per day for a further 4 months (the dose may be increased if the subject tolerated 600 mg in GBT440-001).

Assessments	Enrolment	Outpatient Treatment Period									
		Last treatment day GBT440-001 (+6 days) a	1 +/-3 days a	30 +/-3 days	45 +/-3 days ^g	60 +/-3 days	90 +/-3 days	120+/-3 days	127 +/-3 days	134+/-5 days	148 End
Visit number	0	1	2		3	4	5	6	7	8	
Informed consent	X	X									
Eligibility assessment	X	X									
Medical History	X										
Physical examination b	X		X	X	X	X	X				X
Weight	X		X	X	X	X	X				X
Vital signs	X		X	X	X	X	X				X
12 Lead ECG (single) c	X		X		X	X	X				X
Drug administration d	X-----					X-----					
Adverse events	X-----										X
Urinalysis e	X			X		X	X				X
Urine microalbumin/creatinine	X						X				X
Haematology e	X		X	X	X	X	X				X
Serum biochemistry e	X		X	X	X	X	X				X
Coagulation e	X			X		X	X				X
Pregnancy test (females only)	X		X		X	X	X				X
Haemoglobin electrophoresis					X	X					X
PK samples (plasma and whole blood) f	X		X		X	X	X	X	X	X	X
Serum erythropoietin	X ^g		X		X	X	X	X			X
Exploratory plasma biomarkers	X ^g		X		X	X	X				X
Dense cells	X ^g		X		X	X	X				X
Carboxyhaemoglobin	X ^g				X						X
HbA1c	X ^g					X					X
NT-proBNP	X ^g					X					X
Modified SCD severity questionnaire	X		X		X	X	X	X			X
Concomitant medication diary	X-----										-X

Key

- a: Enrolment and visit 1 may be combined. On admission to the clinic the subjects will be asked whether they want to be considered for study GBT440-024. If the subject is interested in being enrolled on study GBT440-024 all consent activities will be completed before the samples/procedures for GBT440-001 or GBT440-024 are collected/Performed. Visit 0 (enrolment visit) is the last day of treatment in GBT440-001, which can be 6 days before Visit 1. If the last day of treatment in GBT440-001 (Day 118 or Day 60 for Cohort 17 and Cohort 15) – the enrolment visit is not being repeated as standalone visit.
- b: Complete physical examination on enrolment, a limited physical examination on all other days. Directed physical examinations will be performed as required.
- c: 12 lead ECG (single) will be performed within 30 minutes prior to dose
- d: GBT440 600mg (two capsules) will be administered daily in the morning. On days when PK samples are drawn GBT 440 should be administered after an overnight fast.

During the dosing period, subjects will be contacted every week in between outpatient visits to confirm GBT440 administration and subject well-being.

- e: PK samples will be drawn pre dose. . If the dose is increased to 1500 mg, please collect the following timepoints: pre dose, then 1-4 hours, 6-8 hours and 24 hours post dose on study visit days of Day 15 (± 3 days), Day 60 (± 3 days) and Days 90 (± 3 days) of receiving 1500 mg.
- f: Days 45 are only to be conducted if the dose is increased to 1500 mg.
- g: Can be omitted if measurements were collected in the past 7 days as part of the GBT440-001 study.

[figure not shown]

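### Table 4 schedules no haematology, biochemistry, coagulation or urinalysis on Day 60, the last treatment day for Group 1

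*Combined protocol and SAP*

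**What the plan says.** Table 4 has nine columns: Enrolment and Days 1, 15, 30, 45, 60, 67, 74 and 88. Drug administration ends at Day 60. The safety laboratory rows read "Haematology e X X X X X" and "Serum biochemistry e X X X X X", and neither has a mark under Day 60. By contrast, "Serum erythropoietin X ^h X X X" does have one.

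Footnote g restricts two of the laboratory visits: "Days 15 and 45 are only to be conducted if the dose is increased to 1500 mg". Footnote e leaves further sampling to clinical need: "Additional samples will be collected if clinically indicated".

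In Table 5 (Groups 2, 4 and 5) the haematology row is "Haematology e X X X X X - X X X X X", with a mark on Day 180, the last treatment day of those groups, and a dash at Day 60. In Table 6 (Group 3) it is "Haematology e X X X X X X X", which as extracted includes the last treatment day, Day 120.

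Section 6.1 makes safety and tolerability over six cumulative months of dosing the primary objective. Section 6.2 makes the haemolysis biomarkers a secondary objective. Section 11.2.1 says those markers are measured according to the schedule, and Section 12.4 summarises them at every time point. Section 5.3 singles out erythropoietin, haemoglobin and reticulocytes for watching hypoxia and hyperviscosity.

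**The concern.** Day 60 is where Group 1 completes the exposure that the primary objective is about. Table 3 places haemoglobin and reticulocytes in the haematology panel, and bilirubin and LDH in the biochemistry panel. If neither panel is drawn, the Day 60 PK, erythropoietin and dense-cell results have no haemoglobin, reticulocyte, bilirubin or LDH value from the same day to be read against. There is also no safety laboratory panel at the end of treatment.

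Day 88 cannot stand in for Day 60, because by then the subject has been off drug for four weeks. A sample that was not taken cannot be recovered at analysis. No reason is given for treating Group 1 differently from the groups in Table 5.

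**Working it through.** The plan states no figure to reproduce on this point. The check is a reading of the schedule by cell position, followed by simple day counts.

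**Table 4, rows mapped to its nine columns** (each row below has exactly nine cells):

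| Row | Marked at | Day 60 |
|---|---|---|
| Haematology | Enrolment, 15, 30, 45, 88 | blank |
| Serum biochemistry | Enrolment, 15, 30, 45, 88 | blank |
| Coagulation | Enrolment, 15, 45, 88 | blank |
| Urinalysis | Enrolment, 15, 45, 88 | blank |
| Weight | Enrolment, 15, 30, 45, 60, 88 | marked |
| ECG | 30, 60, 88 | marked |
| Erythropoietin, dense cells | Enrolment, 30, 60, 88 | marked |
| PK | Enrolment, 30, 60, 67, 74, 88 | marked |

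Rows that are marked at Day 60 align under the same header, so a shift of the whole table is unlikely.

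**Exposure at Day 60.** Cohort 17's last treatment day in GBT440-001 is Day 118 (note to Table 5). 118 + 60 = 178 days, and 178 / 30.44 = 5.8 months, the nominal six.

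**A Group 1 subject whose dose is not increased.** With Days 15 and 45 removed by footnote g:
- On-drug haematology and biochemistry after enrolment: Day 30 only.
- On-drug coagulation and urinalysis after enrolment: none. The enrolment sample itself may be on drug.
- Day 30 to end of treatment: 60 − 30 = 30 days. With the ±3-day windows, 57 − 33 = 24 to 63 − 27 = 36.
- Day 30 to the next panel: 88 − 30 = 58 days. With the Day 30 window, 88 − 33 = 55 to 88 − 27 = 61 (Day 88 prints no window).
- Of those 58 days, 88 − 60 = 28 are off drug.

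**Markers without a Day 60 value.** Section 11.2.1 lists five types: haemoglobin, unconjugated bilirubin, LDH, reticulocytes and dense cells. Only dense cells are scheduled, so 4 of 5 are missing. Of the three markers named in Section 5.3, only erythropoietin is scheduled, so 2 of 3 are missing.

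**Comparators.** Table 5 has 14 columns and 14 cells in each of the four laboratory rows, and all four panels are marked at Day 180. Table 6 has 10 visit columns but 11 cells in the haematology row. Read from the left, Day 120 is marked. That alignment fits the visit-number, ECG and pregnancy rows, which are all blank in the fourth cell (the conditional Day 45 visit).

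**Size of Group 1.** Section 5.2.1 gives 8 subjects in Cohort 17, including placebo. At 03 August 2016 two had enrolled in this study and two were still dosing. 2 + 2 = 4 is the upper end, if all four were on active drug and enrolled without a gap of more than 7 days. The lower end is 0, because allocation is not given.

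**Timing.** Day 1 on 03 August 2016 puts Day 60 on 01 October 2016, 3 days after Version 2 (28 September 2016).

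**The case against.** The strongest objection concerns scale. The on-drug interval without a panel is 30 days, the same spacing that Table 5 uses from Day 90 to Day 180, so what is lost is an end-of-treatment value rather than the normal frequency of monitoring. Vital signs, weight, ECG, erythropoietin, PK and dense cells are still scheduled at Day 60, adverse events are collected throughout, and subjects are contacted weekly. The analysis is descriptive, the sample size has no statistical basis, and Group 1 may be empty or already past Day 60. Version 2 was also written to allow titration, and Section 8.2.1 brings subjects back every two weeks for laboratory work while the dose is being raised. All of this is correct and limits the size of the point. It does not supply the missing values.

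The second objection concerns extraction. Nine cells do not rule out a shift within a row: moving the middle marks of coagulation and urinalysis one column to the right would give the erythropoietin pattern. Table 5, however, also marks coagulation at Days 15 and 45, which supports Table 4 as printed. Table 6 is a weak comparator. It has a surplus cell, and the left alignment puts erythropoietin at Day 127, after the last dose. The conclusion therefore rests on Table 5 and needs nothing from Table 6.

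Third, other provisions might fill the gap. Footnote e and the note under Table 3 permit extra tests, but only on clinical indication or at the investigator's discretion. The safety committee's review, at least monthly, draws no sample; with 58 days between panels, at least one review has no new scheduled panel for the subject. The two-weekly visits in Section 8.2.1 do not appear in Table 4, do not name the panels and do not guarantee a Day 60 value. No gap is claimed for titrated subjects because of them.

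**Conclusion.** The concern holds. As Table 4 is printed, a Group 1 subject whose dose is not increased reaches the six-month total with no scheduled haematology, biochemistry, coagulation or urinalysis on the last treatment day. Four of the five haemolysis-marker types and two of the three Section 5.3 markers are missing at that point.

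This affects few subjects, about 0 to 4 of at most 16 by inference, and no test or decision rule depends on it. It should still be corrected, because the gap falls at the time point of the primary objective, is unexplained and cannot be repaired afterwards. For anyone who started by 03 August 2016 the correction may come too late.

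Confidence is moderate. The conclusion assumes that the extracted table matches the source page, which should be checked.

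Two smaller points should be reconciled. The Day 60 physical-examination cell in Table 4 is also blank, but footnote b ("Complete physical examination on enrolment, a limited physical examination on all other days") may already cover it. The dash for haematology at Day 60 in Table 5 is probably a slip, since biochemistry is drawn there.

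**What to change.** After checking the source page:

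- **Table 4:** mark haematology, serum biochemistry, coagulation and urinalysis at Day 60 for every Group 1 subject, independent of footnote g. Reconcile the blank physical-examination cell with footnote b.
- **Section 8.2.1 with Tables 4 and 5:** reconcile the two-weekly visits with the schedules, and state which panels the laboratory assessments comprise.
- **Separate SAP:** for any Group 1 subject already past Day 60 without these samples, report the end-of-treatment value as missing and label Day 88 as off-drug follow-up.
- **Table 5:** replace the haematology dash at Day 60 with a mark.

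The cost is small. Table 4 gains 2.0 + 3.5 + 1.8 = 7.3 mL of blood at most, plus a urine sample, at a visit that already draws blood; Table 5 gains 2.0 mL. Draws in Table 4 become 5 + 1 = 6 for haematology, 5 + 1 = 6 for biochemistry and 4 + 1 = 5 for coagulation, within the limits of 10, 10 and 8 in the blood-volume table of Section 9.0. No visit is added and no dosing rule changes.

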9.0 STUDY PROCEDURES

Table 2 Estimated Blood Volumes:

Assessment	Sample Volume (mL)	No. of Samples	Total Volume (mL)
Sickle Cell Disease Subjects: Multiple Dose			
Safety			
Serum Biochemistry	3.5	Up to 10	35.0
Coagulation	1.8	Up to 8	14.4
Haematology	2.0	Up to 10	20.0
Pregnancy	3.5	8	28.0
Hba1c	3.5	7	24.5
Pharmacokinetic			
GBT440	2.0	11	22.0
Pharmacodynamic			
Serum erythropoietin (EPO)	3.5	Up to 8	28.0

Assessment		Sample Volume (mL)	No. of Samples	Total Volume (mL)
	Frozen Plasma Reserved for immunology/inflammation and exploratory markers	5.0	Up to 8	40.0
	Haemoglobin electrophoresis	2.0	Up to 4	8.0
	Carboxyhaemoglobin	2.0	Up to 7	14.0
Disease Related				
	Dense Cells	2.0	Up to 8	16.0
	NT pro-BNP	2.0	Up to 8	16.0
Total [b]				335.9

Sample volumes are based on direct venipuncture.

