9.2 Pharmacodynamic/Treatment Response Assessments

Sample collection and assessment times are included in the schedule of events (see Section 17.0).

9.2.1 Haemolysis markers:

Haemoglobin, unconjugated bilirubin, LDH, absolute and % reticulocyte counts and % dense cells will be measured.

9.2.2 Disease Related Assessments:

Inflammatory markers and exploratory biomarkers related to SCD disease severity will be assessed and may include, but are not limited to:

- Serum erythropoietin
- Urine microalbumin
- Plasma cytokines or other exploratory markers of SCD
- Haemoglobin F levels
- Immune and Inflammatory plasma biomarkers (e.g. inflammatory cytokines)

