12.1 Sample Size Determination

This is an extension study following on from GBT440-001. The sample size has therefore not been subject to any statistical considerations.

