12.4 Pharmacodynamic/Efficacy Analysis

Haemolysis and Disease related assessments will be listed and summarised at each time point using appropriate descriptive statistics.

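### Haemoglobin electrophoresis has no pre-treatment sample in placebo roll-over Groups 2 and 4, and no on-treatment sample in Group 1

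*Combined protocol and SAP*

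**What the plan says.** Section 9.2.2 includes "Haemoglobin F levels" in an open list of exploratory disease-related markers. The Section 17.0 schedules have no separate row for haemoglobin F, so I take the row "Haemoglobin electrophoresis" to be its source.

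- **Table 4 (Group 1).** These subjects come from active treatment and "will continue receiving GBT440 900 mg per day for a further 2 months". Drug administration is marked at Day 1 and Day 60. Electrophoresis is marked once, at Day 88.
- **Table 5 (Groups 2, 4 and 5).** There are two starting columns. Enrolment is the last treatment day of GBT440-001 for Cohorts 15 and 17. The other is headed "Baseline for Cohort 7,11,12,14, 16 or 17 (within 7 days of Day 1" and serves returning subjects. Electrophoresis is marked in the second column and at Days 90, 180 and 208. Enrolment and Day 1 are blank.
- **Table 6 (Group 3).** Enrolment is blank. Two on-treatment visits and the end visit (Day 148) are marked.

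Footnote h of Table 5 waives certain enrolment samples: "Can be omitted if measurements were collected in the past 7 days as part of the GBT440-001 study". It is attached to other markers in the Enrolment column, such as dense cells and carboxyhaemoglobin, and not to electrophoresis.

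The estimated blood volumes table in Section 9.0 budgets "Haemoglobin electrophoresis 2.0 Up to 4 8.0" (mL per sample, number of samples, total mL). Section 12.4 states the analysis: "Haemolysis and Disease related assessments will be listed and summarised at each time point using appropriate descriptive statistics".

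**The concern.** The study is open label with a single arm (Sections 7.1 and 8.7), so a subject's own earlier value is the only natural comparator for a biomarker. The protocol mostly follows that logic. Group 5 has a baseline electrophoresis sample, and carboxyhaemoglobin, HbA1c and NT-proBNP have an enrolment mark in all three tables. Electrophoresis in the roll-over groups departs from this pattern with no reason given.

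The gap matters most in Groups 2 and 4. These subjects received placebo in GBT440-001, so Visit 0 is the last scheduled chance to sample them before GBT440, and a missed sample cannot be recovered. Group 5's baseline cannot stand in for theirs. Cohort 15, the source of Group 4, is HbSC and HbS/β⁺thalassaemia (Section 5.2.1), while the study as a whole admits four genotypes (Section 7.2.1). In Group 1 the one value describes subjects about four weeks off drug, with nothing in the study to set beside it.

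Haemoglobin F is not an incidental marker here: Sections 5.0 and 5.3.1 derive the 20-30% occupancy target from subjects with persistent haemoglobin F.

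**Working it through.** **Inputs.** The electrophoresis and drug administration rows of Tables 4, 5 and 6 (Section 17.0); volume and number of samples from the blood volumes table (Section 9.0); group definitions (Sections 7.1 and 8.6). No alpha, power or effect size enters, because the study has none: "The sample size has therefore not been subject to any statistical considerations".

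**Step 1: count the marks per subject.**

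| Group | Off drug, before dosing in this study | On treatment | After end of dosing | Total |
|---|---|---|---|---|
| 1 (Table 4) | not possible (arrives on drug) | 0 | 1 (Day 88) | 1 |
| 2 and 4 (Table 5, Enrolment) | 0 | 2 (Days 90, 180) | 1 (Day 208) | 3 |
| 3 (Table 6) | not possible (arrives on drug) | 2 | 1 (Day 148) | 3 |
| 5 (Table 5, Baseline) | 1 | 2 (Days 90, 180) | 1 (Day 208) | 4 |

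**Step 2: reproduce the plan's own figure.** The largest count is 4, and 4 × 2.0 mL = 8.0 mL. This matches the blood volumes table, which supports this reading of the marks.

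**Step 3: time off drug at the last sample.** End visit minus last dosing day:
- Group 1: 88 − 60 = 28 days. With the ±3 day window on Day 60, the range is 88 − 63 = 25 to 88 − 57 = 31 days.
- Groups 2, 4 and 5: 208 − 180 = 28 days.
- Group 3: 148 − 120 = 28 days.

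**Step 4: which contrasts exist within this study.**
- Group 1: one value, so no change of any kind.
- Groups 2 and 4: Day 90 to Day 180, and on drug to 28 days off drug. There is no change from baseline.
- Group 3: on-treatment values against Day 148. An enrolment sample would follow two months of GBT440, so only an on-drug starting reference is missing.
- Group 5: change from baseline is available.

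**Step 5: effect of the fix.** Adding Visit 0 in Groups 2 and 4 gives 3 + 1 = 4 samples. Adding Day 60 in Group 1 gives 1 + 1 = 2. The maximum stays at 4 samples and 8.0 mL. If the optional enrolment mark is also added, Group 1 has 3 and Group 3 has 4, still within the allowance.

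**Step 6: how many subjects.** Group sizes are not stated. Section 5.2.1 gives 6 active to 2 placebo for Cohorts 7, 14 and 16, each of eight subjects. Assuming the same split in Cohorts 15 and 17, Groups 2 and 4 together hold 0 to 2 + 2 = 4 subjects and Group 1 holds 0 to 6, under the study cap of 16. Several Cohort 17 subjects finished before this study opened, and two had enrolled by 03 August 2016, so the true numbers are probably lower.

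**The case against.** The best case for leaving the schedule alone has four parts.

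1. **Parent-study data.** Direct roll-overs may have an interruption in dosing of no more than 7 days (Section 7.2.1), and Table 5 asks for a baseline sample only from returning subjects. That fits reliance on GBT440-001 values. However, footnote h, the protocol's device for such reliance, is not attached to this row, and the document does not say that GBT440-001 collected electrophoresis. An earlier value can be neither assumed nor excluded, so the point is limited to this study's own samples.
2. **No planned analysis fails.** The marker is exploratory and optional, and Section 12.4 promises only descriptive summaries by time point. This stands and sets the low priority.
3. **Few subjects are affected.** This also stands.
4. **Table reading.** The tables were machine-read. Table 6's header and body are shifted by one column, so its on-treatment marks are Days 60 and 90 or Days 45 and 60; Enrolment is blank either way. Table 4 as read also shows no Day 60 haematology mark, a reason to check the source layout. Cohort 17 appears in both starting columns of Table 5, so placing Group 2 under Enrolment rests on reading it as a direct roll-over group.

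A reader might also infer three stronger points that the documents do not support:
- *No change in haemoglobin fractions can be estimated anywhere.* Group 5 has a baseline, and Groups 2 to 4 each have later samples that can be compared.
- *Day 88 values would be reported as response.* Day 88 has its own column and summaries are by time point, so nothing in the plan says this.
- *The other Group 1 markers without a Day 60 mark (urine microalbumin, carboxyhaemoglobin, HbA1c, NT-proBNP) share the defect.* They have an enrolment value taken on drug, so an on-drug versus off-drug contrast exists. A Day 60 sample for them is a sampling preference.

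**Conclusion.** The point holds within limits. From this study's own electrophoresis samples, change from baseline cannot be estimated in Groups 2 and 4 (three samples, none before GBT440), and no change can be estimated in Group 1 (one sample, 28 days after dosing ends, range 25 to 31). Group 5 is unaffected. Group 3 lacks only an on-drug starting reference.

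This assumes that the source tables match the extracted layout, that Group 2 uses the Enrolment column, and that electrophoresis is the source of the haemoglobin F result. It makes no claim about what GBT440-001 collected.

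No objective or planned summary fails without the change. It is a cheap improvement to an exploratory marker, worth making mainly because the pre-dose sample in Groups 2 and 4 cannot be obtained later.

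**What to change.** First check the source layout of Tables 4 to 6. Then:

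- **Table 5:** mark electrophoresis in the Enrolment column (Visit 0) for Groups 2 and 4 and attach footnote h, so that a GBT440-001 value from the past 7 days can serve instead.
- **Table 4:** mark electrophoresis at Day 60 for Group 1, giving an end-of-treatment value to compare with Day 88.
- **Optional:** add an Enrolment mark for Groups 1 and 3, labelled as an on-drug reference and not a baseline.

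If GBT440-001 did collect electrophoresis and the sponsor prefers to use those values, the protocol should say so and name the reference visit.

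The required changes cost one extra 2 mL tube per affected subject. No visit is added: Visit 0 already has blood sampling, and Table 4 already marks PK, erythropoietin, exploratory biomarkers and dense cells at Day 60. The 4-sample, 8.0 mL allowance in Section 9.0 needs no change. For any subject already dosed in Group 2 or 4 without a Visit 0 sample, the change comes too late, and the report should say that no pre-treatment value exists from this study.
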